6.2 Exclusion Criteria

The presence of any of the following will exclude a participant from enrollment.

1) Target Disease Exclusion

[figure not shown]
- a) Participants with any of the following specific CLE subtypes in isolation: ACLE, lupus tumidus, lupus (profundus) panniculitis, chilblains.
- b) Participants with forms of drug-induced CLE and/or drug-induced SLE
- c) Participants with active kidney disease, defined as an estimated glomerular filtration rate (eGFR) of < 60 mL/min/1.7 m² and/or proteinuria > 0.5 g/24 h (spot urine protein/creatinine ratio [UPCR]: > 56.5 mg/mmol).
- d) Participants with antiphospholipid antibody syndrome, serious thrombotic event (eg, pulmonary embolism, saddle embolism, stroke, deep vein thrombosis) or unexplained pregnancy loss within 1 year before the Screening Visit. Participants with a history of 3 or more unexplained consecutive pregnancy losses.
- e) Participants with active severe or unstable neuropsychiatric SLE including, but not limited to, aseptic meningitis; cerebral vasculitis; myelopathy; demyelination syndromes (ascending, transverse, acute inflammatory demyelinating polyradiculopathy); acute confusional state; impaired level of consciousness; psychosis; acute stroke or stroke syndrome; cranial neuropathy; status epilepticus; cerebellar ataxia; and mononeuritis multiplex.
- f) **Not applicable per Protocol Amendment 02:** Participants with other autoimmune diseases (eg, multiple sclerosis, psoriasis, irritable bowel disease [IBD], etc) with the exception of those with Type 1 autoimmune diabetes mellitus, thyroid autoimmune disease, celiac disease, or secondary Sjögren's syndrome.
- g) Participants with other non-SLE driven inflammatory joint or skin disease or overlap syndromes as primary disease (eg, dermatomyositis, fibromyalgia, polymyositis, scleroderma, mixed connective tissue disease, rosacea, sarcoidosis, Sjögren's syndrome) that in the opinion of the investigator will significantly impact the assessment of CLE/SLE disease manifestations and activity.
- h) Participants with other autoimmune diseases (eg, multiple sclerosis, psoriasis, etc) with the exception of those with Type 1 autoimmune diabetes mellitus, thyroid autoimmune disease, celiac disease, or secondary Sjögren's syndrome.

2) Other Medical History and Conditions

- a) Women who are pregnant or breastfeeding.
- b) Any major illness/condition or evidence of an unstable clinical condition (eg, renal, hepatic, hematologic, gastrointestinal, endocrine, pulmonary, immunologic, psychiatric) or local active infection/infectious illness that, as determined by investigator, will substantially increase the risk to the participant if he or she participates in the study.

- c) Any major surgery within the last 30 days before the first dose of study treatment, or any surgery planned during the course of the study.
- d) Participants with cancer or history of cancer or lymphoproliferative disease within the previous 5 years except for:
 - i) treated (eg, cured) basal cell or squamous cell in situ skin carcinomas
 - ii) treated (eg, cured) cervical intraepithelial neoplasia or carcinoma in situ of the cervix with no evidence of recurrence within 5 years of the Screening Visit.
- e) Class III or IV congestive heart failure as defined by the New York Heart Association (NYHA) or any recent onset of heart failure resulting in NYHA Class III/IV symptoms.
- f) Acute coronary syndrome (eg, myocardial infarction, unstable angina pectoris) and/or any history of significant cerebrovascular disease within 24 weeks before Screening Visit.
- g) Current or recent (within 3 months before Screening Visit) gastrointestinal disease, including gastrointestinal surgery, that could impact the absorption of study treatment.
- h) Participant with non-SLE concomitant illness, as determined by investigator, who is likely to require additional systemic glucocorticosteroid therapy during the study (eg, asthma).
- i) Significant blood loss (> 500 mL) or blood transfusion within 4 weeks before Screening Visit.
- j) Inability to take medication orally.
- k) Inability to undergo venipuncture and/or tolerate venous access.
- l) Any other sound medical, psychiatric, and/or social reason as determined by investigator.
- m) Recent (within 6 months before randomization) drug or alcohol abuse as defined by the Diagnostic Criteria for Drug and Alcohol Abuse in the Diagnostic and Statistical Manual of Mental Disorders IV ([Appendix 10](#)).
- n) History of any significant drug allergy (such as anaphylaxis or hepatotoxicity).
- o) History of congenital or acquired immunodeficiency.

3) Prior and Concomitant Therapy

- b) Required discontinuation periods to allow previous exposure to other immunomodulatory or biologic drugs are provided [REDACTED]. If a drug is not specifically listed, consult the medical monitor for guidance. Participant has enrolled in a clinical trial and has

received an investigational product within 5 pharmacokinetic half-lives or one month, whichever is longer, prior to the Screening Visit.

- c) Inability to comply with restrictions and prohibited treatments (Section 7.7.1); inability to comply with medication discontinuation requirements listed [REDACTED].
- d) **Not applicable per Protocol Amendment 02:** Participant has used high or mild potency topical corticosteroids (WHO Class 1-5) [refer to Appendix 12], intralesional CS topical immunosuppressants (calcineurin inhibitors), or topical retinoids within 2 weeks prior to Screening Visit.
- e) Participant has used intramuscular, intralesional/intradermal, intra-articular, intrabursal, and/or intravenous (IV) CS within 6 weeks prior to Screening Visit.
- f) Participants using modified-release oral CS formulations.
- g) Participants using drugs inducing cutaneous lupus erythematosus [REDACTED].
- h) **Not applicable per Protocol Amendment 02:** Participants that have received a live vaccine within 90 days or an inactivated vaccine within 30 days before Screening Visit.
- i) Participants that have received live vaccine within 60 days prior to Screening Visit.
- j) Participant has used high or moderate potency topical corticosteroids (WHO Class 1-5; refer to Appendix 12), topical immunosuppressants (calcineurin inhibitors), or topical retinoids within 2 weeks prior to Screening Visit.

4) Physical and Laboratory Test Findings

- a) Clinically significant abnormalities on chest X-ray or ECG at Screening Visit.
- b) Clinically significant abnormalities in laboratory tests at Screening Visit including the following:
 - i) Serum alanine aminotransferase (ALT) $> 2 \times$ ULN or serum aspartate aminotransferase (AST) $> 2 \times$ ULN.
 - ii) Serum total bilirubin $> 1.5 \times$ ULN, unless due to documented Gilbert's syndrome.
 - iii) Hemoglobin < 9 g/dL (90 g/L).
 - iv) Estimated glomerular filtration rate < 60 mL/min.
 - v) Absolute white blood cell count $< 2.0 \times 10^3/\mu\text{L}$ ($2.0 \times 10^9/\text{L}$).
- [REDACTED]
- vii) Any other significant laboratory or procedure abnormalities, as determined by investigator that might pose unacceptable risk to the participant during the study.

5) Findings Related to Possible Infection

- a) Participants with any of the following tuberculosis (TB) criteria:
 - i) History of active TB prior to Screening Visit, regardless of completion of adequate treatment.
 - ii) Signs or symptoms of active TB (eg, fever, cough, night sweats, and weight loss) during Screening as judged by the investigator.

- iii) Any imaging of the chest (eg, chest x-ray, chest computed tomography scan) obtained during the Screening period or anytime within 6 months prior to Screening with documentation, showing evidence of current active or history of active pulmonary TB.
- iv) **Not applicable per Protocol Amendment 02:** Latent TB infection (LTBI) defined as positive IGRA, by QuantiFERON-TB Gold testing at Screening, in the absence of clinical manifestations.

Not applicable per Protocol Amendment 02: Note: Participants are eligible if:

There are no current signs or symptoms of active TB.

-AND-

- (1) **Not applicable per Protocol Amendment 02:** Participant has received adequate documented treatment for LTBI within 5 years of Screening.

-OR-

- (2) **Not applicable per Protocol Amendment 02:** Participant has initiated prophylactic treatment for LTBI per local guidelines.

- (a) **Not applicable per Protocol Amendment 02:** Participants not currently on prophylactic treatment per local guidelines, including participants that have documented completed treatment within 5 years of Screening: indeterminate results of initial IGRA with no signs or symptoms of active TB must be retested for confirmation.

- (i) **Not applicable per Protocol Amendment 02:** If the second test is again indeterminate, the participant will be excluded from the study. If the retest is positive, the participant will be excluded. If the retest is negative, the participant may be eligible provided no other exclusion criteria for TB are met.

- (b) **Not applicable per Protocol Amendment 02:** Participants that are on prophylactic treatment for LTBI per local guidelines, and there are no current signs or symptoms of active TB, retesting of an initial positive or indeterminate result is not required and participants may be eligible provided no other exclusion criteria for TB are met, and participants continue to complete treatment for LTBI per local guidelines

- v) Latent TB infection (LTBI) defined as positive IGRA, by QuantiFERON-TB Gold testing at Screening, in the absence of clinical manifestations, or known positive Quantiferon-TB Gold testing by history

Note: Participants may be eligible if:

- (1) There are no current signs or symptoms of active TB

-AND-

- (2) Participant has received adequate documented treatment for LTBI within 5 years of screening

OR

- (3) Participant has initiated prophylactic treatment for LTBI per local guidelines and is rescreened after 1 month of treatment. To continue in the study, the participant must agree to complete a locally recommended course of treatment for LTBI. The

BMS Clinical Trial Physician/Medical Monitor should be consulted on all LTBI cases.

Note: An IGRA test that is indeterminate with no signs or symptoms of active TB must be retested for confirmation. If the second result is indeterminate, the participant will be excluded from the study. If the retest is negative, the participant may be eligible provided no other exclusion criteria for TB are met. If the retest is positive, the participant may be treated as having LTBI with initiation of prophylactic treatment (as above).

(4) **Not applicable per Protocol Amendment 02:** Participants with evidence of hepatitis B or hepatitis C infection determined by serologic testing (described in [Section 9.4.5](#)) at Screening Visit will be excluded. Participants with isolated positive hepatitis B surface antibody are not excluded (refer to [Appendix 14](#)).

- b) **Not applicable per Protocol Amendment 02:** Positive for human immunodeficiency virus (HIV) by antibody testing (HIV-1 and -2 Ab) at Screening Visit. **Note:** Participants who are newly found to be HIV-positive should be directed to appropriate follow-up care.
- c) **Not applicable per Protocol Amendment 02:** Currently on any therapy for chronic infection (eg, pneumocystis, cytomegalovirus, herpes simplex, herpes zoster, invasive bacterial or fungal infections, or atypical mycobacteria).
- d) **Not applicable per Protocol Amendment 02:** Known active infection, or any major episode of infection requiring hospitalization or treatment with parenteral (intramuscular or IV) antimicrobial agents (eg, antibiotics, antiviral, antifungal, or antiparasitic agents) within 30 days of randomization, or completion of oral antimicrobial agents within 2 weeks of randomization.
- e) **Not applicable per Protocol Amendment 02:** Previous history of herpes zoster, herpes simplex, or influenza infection within 12 weeks before randomization or a history of disseminated/complicated herpes zoster infection (multidermatomal involvement, ophthalmic zoster, central nervous system involvement, or post-herpetic neuralgia).
- f) **Not applicable per Protocol Amendment 02:** Severe infection within 4 weeks prior to screening.
 - i) **Not applicable per Protocol Amendment 02:** Additionally, in the case of prior SARS-CoV-2 infection, symptoms must have completely resolved and based on investigator assessment in consultation with the clinical trial physician, there are no sequelae that would place the participant at a higher risk of receiving investigational treatment.
- g) Participants with evidence of hepatitis B or hepatitis C infection determined by serologic testing (described in [Section 9.4.5](#)) at Screening Visit will be excluded. Participants with isolated positive hepatitis B surface antibody are not excluded (refer to [Appendix 14](#)).
- h) Positive for human immunodeficiency virus (HIV) by antibody testing (HIV-1 and -2 Ab) at Screening Visit. **Note:** Participants who are newly found to be HIV positive should be directed to appropriate follow-up care.
- i) Currently on any therapy for chronic infection (eg, pneumocystis, cytomegalovirus, herpes simplex, herpes zoster, invasive bacterial or fungal infections, or atypical mycobacteria).
- j) Known active infection, or any major episode of infection requiring hospitalization or treatment with parenteral (intramuscular or IV) antimicrobial agents (eg, antibiotics,

antiviral, antifungal, or antiparasitic agents) within 30 days of randomization, or completion of oral antimicrobial agents within 2 weeks of randomization.

- k) Previous history of herpes zoster, herpes simplex, or influenza infection within 12 weeks before randomization or a history of disseminated/complicated herpes zoster infection (multidermatomal involvement, ophthalmic zoster, central nervous system involvement, or post-herpetic neuralgia).
- l) Known active infection, or any major episode of infection requiring hospitalization or treatment with parenteral (intramuscular or IV) antimicrobial agents (eg, antibiotics, antiviral, antifungal, or antiparasitic within 4 weeks prior to screening).

Note: In the case of prior SARS-CoV-2 infection, symptoms must have completely resolved and based on investigator assessment, that could place the participant at risk when receiving IP. SARS-CoV 2 testing may be conducted prior to randomization if required by and in accordance with national, local, or institutional guidelines.

6) Other Exclusion Criteria

- a) Inability to abstain from the use of tanning salons or prolonged intentional sun exposure from Screening to Week 52. Usual and reasonable sunlight exposure during daily activities is acceptable.
- b) Prisoners or participants who are involuntarily incarcerated. (Note: under certain specific circumstances and only in countries where local regulations permit, a person who has been imprisoned may be included or permitted to continue as a participant. Strict conditions apply and Bristol-Myers Squibb approval is required.
- c) Participants who are compulsorily detained for treatment of either a psychiatric or physical (eg, infectious disease) illness.

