9.4.1 Physical Examinations

Schedules for physical examinations are provided in [Section 2](#). Complete and/or targeted PEs may be performed by a Doctor of Medicine (MD), or someone who is authorized to perform the examinations by training and has been delegated this task by the principal investigator. While the targeted examination may not be as comprehensive as the initial full examination, key aspects should evaluate important body systems as clinically indicated. These body systems can include lymph nodes, liver, spleen, and breast at the discretion of the examiner. A targeted examination may note any changes in the participant's condition (body systems) since the last assessment and does not preclude examination of any of the other body systems as clinically indicated. Every effort should be made to ensure the same evaluator will complete the examination for each participant at all visits throughout the study. Documentation of who performed the examination is to be recorded in source notes.

9.4.2 *Tuberculosis Screening and Chest X-ray*

A chest X-ray and PE are part of the process to assess a participant's eligibility as defined in [Section 6.2, Exclusion Criteria, 6\) a\)](#), and outlined in [Section 2](#). A chest X-ray at the Screening Visit is required if not already performed within 6 months of obtaining written informed consent.

In addition to a complete PE and medical history to evaluate exposure to TB, all participants will have a screening test, an IGRA (eg, T-spot® or QuantiFERON®), preferably performed centrally. If unable to obtain central laboratory results (eg, repeated test due to indeterminate result), an IGRA test could be obtained locally, after consultation with the Clinical Trial Physician/Medical Monitor.

9.4.3 *Vital signs*

Refer to Schedule of Activities in Section 2.

9.4.4 *Electrocardiograms*

Refer to Schedule of Activities in Section 2.

9.4.5 *Clinical Safety Laboratory Assessments*

A central laboratory will perform assessments of safety laboratory assessments (except pregnancy tests) and provide reference ranges and laboratory reports. Investigators must document their review of each laboratory safety report. Any laboratory test result that the investigator considers clinically relevant is to be recorded on the appropriate AE page of the CRF ([Section 9.2.7](#)). Results of clinical laboratory tests performed during screening must be available prior to randomization.

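### A first-test positive T-spot, which Section 9.4.2 permits at Screening, does not meet the latent-TB exclusion, which counts only QuantiFERON-TB Gold

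*Combined protocol and SAP*

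**What the plan says.** Section 6.2, criterion 5) a) v), is the current LTBI exclusion. It describes LTBI as "defined as positive IGRA, by QuantiFERON-TB Gold testing at Screening, in the absence of clinical manifestations, or known positive Quantiferon-TB Gold testing by history". It has two limbs, a Screening result and a past result, and both name the same assay. Three things hang on it: an exception for documented earlier treatment, an exception for prophylaxis already begun with rescreening after 1 month, and a consultation with the Medical Monitor on LTBI cases.

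A Note under v) is worded without an assay: "An IGRA test that is indeterminate with no signs or symptoms of active TB must be retested for confirmation". It goes on to say that a second indeterminate result excludes the participant, and that a positive retest can be handled as LTBI.

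Section 9.4.2 describes the test itself: "all participants will have a screening test, an IGRA (eg, T-spot® or QuantiFERON®), preferably performed centrally". If a central result cannot be had, "an IGRA test could be obtained locally, after consultation with the Clinical Trial Physician/Medical Monitor". No assay is specified for that local test.

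**The concern.** The procedure admits an assay whose positive result the exclusion does not recognise. If that assay is used for the first Screening test, the LTBI rule does not fire on a result that the screening step exists to find.

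This is a safety screen. Appendix 14 tells sites that study treatment is expected to have immunosuppressive effects, and the conditions under v) control how a participant with LTBI may enter. Section 6 also rules out eligibility waivers, so sites should be able to apply the criterion exactly as it stands. Here, doing so gives different handling to two positive results from tests that the same protocol permits.

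**Working it through.** The documents state no figure on this point, and no arithmetic applies. The check is to follow each possible IGRA result through the current text.

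| Situation (no symptoms, clear imaging) | Does v) or its Note apply? | Consequence |
|---|---|---|
| First Screening test is QuantiFERON, positive | Yes, Screening limb of v) | LTBI conditions and Medical Monitor consultation apply |
| First IGRA indeterminate, retest positive on any assay | Yes, through the Note | Can be handled as LTBI |
| First Screening test is T-spot, positive | No | LTBI conditions not triggered |
| Past positive QuantiFERON | Yes, history limb of v) | LTBI conditions apply |
| Past positive T-spot, Screening QuantiFERON negative | No | LTBI conditions not triggered |

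The third row is the contradiction between the two sections. I looked for other text that would close it:

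1. **Criteria 5) a) i) to iii).** These concern a history of active TB, signs or symptoms of active TB, and chest imaging that shows active TB, current or past. None refers to an IGRA result.
2. **The Note under v).** It starts from an indeterminate result, so it does not reach a first test that is plainly positive.
3. **Table 2-1.** The TB screening row only refers to Section 9.4.2.
4. **Section 9.4.5.** It lists TB as a screening-only test and gives no rule for a positive result.
5. **The cross-reference in Section 9.4.2.** It sends the reader to Exclusion Criteria 6) a), which is about tanning and sun exposure. The TB criteria are at 5) a).
6. **Criterion 4) b) vii).** It excludes for "Any other significant laboratory or procedure abnormalities, as determined by investigator that might pose unacceptable risk to the participant during the study". This could catch a positive T-spot, but only if the investigator judges it so. Criteria 2) b) and 2) l) are likewise matters of judgement.

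Nothing states that a first-test positive T-spot counts as LTBI.

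The fifth row is a different matter. Section 9.4.2 governs the test done at Screening and does not say which past results count. The narrow history limb is therefore a question about v) on its own terms, not a conflict with Section 9.4.2.

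**The case against.** The best answer is that the situation may rarely or never arise. Section 6 requires laboratory testing to be done by the study's central laboratory, and Section 9.4.2 prefers a central IGRA. A local test is open only when a central result cannot be obtained, and only after the Medical Monitor has been consulted. The one example given for the local route is a repeat after an indeterminate result, and there the Note already covers a positive retest on any assay. Since v) names QuantiFERON, that may simply be what the central laboratory runs.

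Much of this stands, and it limits the point in four ways that a reader might otherwise miss:

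- **Sites do not have a free choice of assay.** A reader might infer this from the T-spot example, but the central-testing default and the consultation step do not support it.
- **Falling outside v) does not make a participant eligible.** The discretionary exclusions remain. They do not impose the LTBI conditions, however, and may be applied differently from site to site.
- **The history limb does not contradict Section 9.4.2.** It may be narrower than intended, and Section 9.4.2 does call for a medical history that looks at TB exposure, so a past T-spot result may well come to light.
- **No count can be derived.** It is tempting to multiply an assumed rate of IGRA positivity by the planned 75 participants. The documents give neither that rate nor the share tested by T-spot, and 75 is the number to be randomized, whereas the exclusion acts on people screened.

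Two replies do not remove the point. The intent to cover any positive IGRA can be guessed, but the words that follow restrict it to one assay. The consultation before a local test is about obtaining that test; it is not a rule on what a positive result means.

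**Conclusion.** The inconsistency is real and is in the current text. A first-test positive T-spot, run centrally or run locally after Medical Monitor consultation, satisfies the screening procedure in Section 9.4.2. In a participant with no symptoms and clear imaging it does not trigger v) or the conditions attached to it, which leaves only discretionary exclusions.

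The number affected is unknown and may be zero if the central laboratory uses only QuantiFERON and no first test is done locally on another assay. The conclusion rests on the literal wording and on the visible text, which does not state the central laboratory's assay. The estimate of treatment effect, power and type I error are not affected. The point deserves correction because it concerns a safety screen and is cheap to settle.

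**What to change.** Reconcile criterion 5) a) v) with Section 9.4.2 so that every IGRA permitted for Screening counts under v). Either of two edits does this, and the choice is the sponsor's:

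- word the Screening limb of v) to refer to any IGRA permitted in Section 9.4.2; or
- restrict Section 9.4.2, including its local-testing route, to the assay named in v).

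In the same edit:

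- confirm whether the history limb is meant to be limited to QuantiFERON, since restricting Section 9.4.2 would not settle that; and
- change the cross-reference in Section 9.4.2 from Exclusion Criteria 6) a) to 5) a).

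The exception conditions and the Note under v) need no change for this purpose.

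The drafting cost is a few words. A protocol change needs ethics committee approval under Appendix 2, so it is best carried in the next amendment. Widening v) could send some T-spot-positive participants through the existing LTBI route or exclude them. Narrowing Section 9.4.2 would remove some flexibility where a central result cannot be obtained.
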